	2) Subjects diagnosed with clinically definite or clinically probable ALS according to revised El Escorial criteria-1998 by the World Federation of Neurology;						
	3) Subjects of $\leq 2$ years after the onset of ALS before randomization;						
Inclusion Criteria	4) The ALSFRS-R scores are all ≥ 2 points, and the respiratory function is 4 points before randomization;						
	5) ALSFRS-R has a decrease of 1-4 points during a 3-month screening period;						
	6) Forced Vital Capacity (%FVC) ≥ 80% before randomization;						
	7) Understand and comply with the study rules, voluntarily participate, and sign an informed consent form (informed consent form is voluntarily signed by the subject himself/herself or his/her legal representative).						
	Subjects who meet one of the following conditions will not be eligible for this trial:						
Exclusion Criteria	1) Familial ALS (judge by family history);						
	2) Those with obvious cognitive impairment (MMSE scale: illiterate group ≤ 19 points, primary school group ≤ 22 points, junior high						

school and above group ( $\geq 8$  years of education)  $\leq 26$  points;

- 3) Obvious dysphagia;
- 4) Severe renal insufficiency: creatinine clearance < 30 mL / min (Cockcroft-Gault formula), or other known severe renal insufficiency disease;
- 5) Severe liver damage: ALT, AST > 3 times the upper limit of normal level, or other known liver diseases such as acute and chronic hepatitis, cirrhosis, etc.;
- 6) Acute myocardial infarction or interventional therapy in the past 6 months, heart failure patients (in accordance with NYHA classification III-IV patients) at the screening period;
- 7) Combined with malignant tumors and serious diseases of blood, digestion or the other systems;
- 8) Allergic to Investigational Product (IMP) or tetramethylpyrazine;
- 9) Female patients during pregnancy and lactation;
- 10) Participate in other clinical studies within 30 days before screening, or is participating in other clinical studies;
- 11) Other circumstances that the investigator considered unsuitable for participation in the study.

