## 540 **3. STUDY DESIGN**

- 541 **3.1.** Overall study design
- The study is designed to be a multi-center, randomized, double-blind, placebo-controlled study
- of efficacy and safety of TBN tablets for the treatment of ALS.
- 544 3.1.1 Design Rationale
- The design basis of this study is as follows:
- 546 (1) General Considerations for Clinical Trials, NMPA, Jan 18, 2017
- 547 (2) Safety Data Rapid Reporting Standards and Procedures During Drug Clinical Trials, NMPA,
- 548 Apr 27,2018
- 549 (3) Chinese Guidelines for Diagnosis and Treatment of Amyotrophic Lateral Sclerosis, Jul, 2012
- 550 (4) Amyotrophic Lateral Sclerosis Developing Drugs for Treatment Guidance for Industry, Feb,
- 551 2018
- As for the screening of subjects, the sponsor requires that incapacitated subjects should obtain
- the consent of their legal guardians to subjects in the test, and vulnerable groups such as children,
- pregnant women, mentally retarded people, mental patients and prisoners should be given special
- protection according to the Good Clinical Practice (GCP) and Methods for ethical review of
- 556 biomedical research involving human beings promulgated by the National Medical Products
- 557 Administration (NMPA).
- In addition, during the design of the protocol, we fully refer to the NDA clinical trial scheme and

results applied by Edaravone, a drug with similar mechanism of action, for the treatment of ALS. ALSFRS-R was the main endpoint index. Patients with a short duration of ALS (within 2 years from onset) and rapid progression (ALSFRS-R functional score decreased by -1 to -4 points within 3 months of screening period) and mild or moderate ALS (The ALSFRS-R scores are all  $\geq$  2 points when enrolled and the respiratory function is 4 points) and well respiratory function (%FCV  $\geq$  80%) are our target subjects. Compared to the control group, the decline of ALSFRS-R scores in Edaravone group were reduced by 2.5 points after a 6 months treatment period, therefore, the treatment period of TBN is designed as 6 months. We anticipate that TBN tablets can benefit patients with early mild ALS by improving motor dysfunction and delaying disease progression.

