#### 603 **3.2. Selection of Study Population**

#### 604 3.2.1 Inclusion Criteria

- Subjects will be enrolled into this trial only if they meet all the following criteria:
- 606 (1) Male or female, aged 45 to 70 years old (including 45 and 70 years old).
- 607 (2) Subjects diagnosed with clinically definite or clinically probable ALS according to revised
- El Escorial criteria-1998 by the World Federation of Neurology.
- 609 (3) Subjects of  $\leq 2$  years after the onset of ALS before randomization.
- 610 (4) The ALSFRS-R scores all  $\geq 2$  points, and the respiratory function is 4 points before
- 611 randomization.
- 612 (5) ALSFRS-R has a decrease of 1-4 points during a 3-month screening period.

- 613 (6) Forced Vital Capacity (%FVC) ≥ 80% before randomization.
- 614 (7) Understand and comply with to the study protocol, voluntarily participate, and sign an
- informed consent form (informed consent form is voluntarily signed by the subject
- 616 himself/herself or his/her legal representative).

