# 5 METHODS FOR REDUCING BIAS: RANDOMIZATION AND BLINDING

#### 5.1 Randomization

975

976

- 977 This study uses Interactive Web Response System (IWRS) to dispense random numbers and
- 978 corresponding IMP. Subjects' random numbers are generated by independent statisticians
- 979 unrelated to the study using SAS 9.4 software or higher version. The subject-drug randomization
- table is in duplicate, sealed and handed over to the main study unit and the sponsor.
- After a 90 day observation period, eligible subjects are to be randomly assigned to high or low
- dose of the IMP group or placebo group (1:1:1). The investigator log into the IWRS system,
- 983 where they are to be given a random number and a drug code.
- In order to ensure that the number of patients in each trial group is similar and the distribution of
- 985 important prognostic factors is balanced, this study uses the minimization method in dynamic
- 986 randomization. The stratification factors are: the diagnostic grade of ALS (clinical diagnosis vs
- 987 clinical diagnosis and laboratory support The diagnostic criteria for clinical diagnosis), the
- 988 change in ALSFRS-R scores during observation period (-1 or -2 vs -3 or -4) and age (<65 years
- 989 vs >65 years).
- 990 Once having been randomly assigned in the study, subjects withdrawing from the clinical trials
- 991 for any reason, regardless of whether or not having been administered with the IMP, will retain
- their random number and the subject will not be allowed to subjects in the trial again.

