# 1368 **8.1 Sample Size Estimation**

- The trial is an exploratory study of safety and efficacy, no statistical assumptions will be made
- and no sample calculations.
- This study is expected to enroll a total of 150 subjects, with 50 in each group.

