# 1398 **8.3.3 Primary Efficacy Endpoint Evaluation**

- 1399 The primary endpoint is difference between the groups in the ALSFRS-R score change from
- baseline at Day 180.
- 1401 ALSFRS-R data of each visit in different treatment groups are statistically described by mean ±
- standard deviation and median (minimum and maximum). Comparing with the baseline, the
- paired T test is to be used to compare the within-group before-after differences. Analysis of
- variance (ANOVA) is used for comparing changes before and after treatment in each group, and
- the linear model will include three random stratification factors. The Tukey method-corrected 95%
- 1406 confidence interval for each group's least squares means (LS Means) and Least Squares Means
- Difference is to be calculated according to the model's least squares means (LS Means) to
- compare the statistical differences between the two groups. The model is to be used to further
- investigate the interaction between groups and three random stratification factors. If there is a
- 1410 qualitative interaction, a subgroup analysis of the relevant random stratification factors will be
- 1411 performed.

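### The primary ALSFRS-R model names no onset-to-baseline progression covariate, though its inputs should be known for every subject: an optional gain in precision

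*Protocol*

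**What the plan says.** Protocol section 8.3.3 compares the groups on change in ALSFRS-R from baseline to Day 180 by analysis of variance, and states that "the linear model will include three random stratification factors". It names no other covariate. Section 5.1 says that "this study uses the minimization method in dynamic" randomisation, and lists the factors as diagnostic grade, the "change in ALSFRS-R scores during observation period (-1 or -2 vs -3 or -4) and age" (under or over 65).

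Three eligibility rules in section 3.2.1 bear on the point:
- Criterion 3 requires at most 2 "years after the onset of ALS before randomization".
- Criterion 4 requires every ALSFRS-R item to score at least 2, "and the respiratory function is 4 points before randomization".
- Criterion 5 reads: "ALSFRS-R has a decrease of 1-4 points during a 3-month screening period".

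The design rationale (section 3.1.1) describes the target as "Patients with a short duration of ALS (within 2 years from onset) and rapid progression". ALSFRS-R is scored again at baseline (section 3.5.2 and the trial schedule). Section 8.1 fixes the size without a calculation: "This study is expected to enroll a total of 150 subjects, with 50 in each group".

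**The concern.** The primary outcome is about six further months of the decline that made each subject eligible, so a subject's earlier rate of loss is a natural predictor of it. The model uses that history only through the screening-period change. This is the difference of two scored visits about 90 days apart, restricted to 1-4 points and then cut to two levels.

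A longer record should be at hand. The ALSFRS-R maximum is 48 (Appendix 2, 12 items of 0-4), so (48 - baseline ALSFRS-R)/months since onset gives the average monthly loss over up to 24 months. Neither this rate nor its two components is named in section 8.3.3. At stake is the width of the primary confidence interval in a trial fixed at 50 per arm and meant to support phase 3 (section 3.1.4).

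**Working it through.** **No stated figure to reproduce.** The protocol gives no SD, effect size or power. The total of 150 is simply 3 x 50.

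**Why both components are needed.** A baseline score of 40 reached in 6 months is (48 - 40)/6 = 1.33 points per month. Reached in 24 months it is 8/24 = 0.33. Equally, 24 months since onset with a baseline of 30 is 18/24 = 0.75, and with a baseline of 47 it is 1/24 = 0.04. A score of 30 is the lowest that criterion 4 allows if all three respiratory items must be 4: 9 x 2 + 3 x 4. Duration without the score is not a rate.

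**Simulation, first set of assumptions.** All parameters are assumed: onset evenly spread over 4-24 months; median past rate 1.0 point per month with log-SD 0.4 or 0.6; scoring error SD 1 or 1.5; screening loss 1-4; baseline 30-47. Persistence is the correlation between log past rate and log current rate. Entries are the fall in residual variance relative to a model with the two-level screening change. Each row covers four runs.

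| Persistence | SD of change | Months alone | Baseline alone | Baseline + months | Rate |
|---|---|---|---|---|---|
| 0.4 | 3.82-4.67 | 0.1-0.2% | 0.2-0.3% | 0.8-1.0% | 0.8-1.0% |
| 0.7 | 3.80-4.62 | 0.3-0.6% | 0.5-1.1% | 3.2-3.7% | 3.3-3.9% |
| 1.0 | 3.75-4.56 | 1.3-1.8% | 1.1-2.8% | 8.9-13.1% | 9.4-15.0% |

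**Second set of assumptions.** Mean slope 0.8 points per month with CV 0.6; onset 6-24 months; slope change between periods of log-SD 0.2-0.6; scoring error SD 0.7-1.5; onset recall error SD 0 or 3 months.
- Rate: 4-44%.
- Baseline plus months: 6-38%.
- Baseline alone: 4-15%.
- Months alone: 0.3-2.2%.

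The large values arise only where the SD of change is about 2.3-3 points. At about 4 points the rate gives roughly 4-9%. Both sets fit the screening-change factor only; age and diagnostic grade were given no effect.

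**What 4-9% buys.** The interval narrows by 1 - sqrt(0.96) = 2.0% to 1 - sqrt(0.91) = 4.6%. This is worth 50/0.96 = 52 to 50/0.91 = 55 subjects per arm.

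**Illustrative power.** Assume SD 5 and a difference of 2.5 points, the edaravone difference that section 3.1.1 cites as background and not as a design target. SE = 5 x sqrt(1 - R2) x sqrt(2/50), where R2 is the fall in residual variance. The Tukey critical value for 3 groups and 144 df is 2.368.

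| R2 | SE | Unadjusted power | Tukey power | Unadjusted 95% half-width |
|---|---|---|---|---|
| 0 | 1.000 | 0.705 | 0.552 | 1.96 |
| 0.05 | 0.975 | 0.727 | 0.578 | 1.91 |
| 0.10 | 0.949 | 0.750 | 0.605 | 1.86 |

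**Cost in degrees of freedom.** The planned model leaves 150 - 1 - 2 - 3 = 144. One more covariate inflates variance by about 1/143 = 0.7%, which roughly cancels the gain in the lowest-persistence row.

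**The case against.** **The planned analysis is valid.** Adjusting for the randomisation factors is sound, and each subject's prospectively observed decline is both a minimisation factor and a model term. Criteria 3 to 5 narrow duration, severity and rate further. The trial is declared exploratory. All of this stands, and it is why the point is an option and not a correction.

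**The SAP may already cover it.** Section 8.3.3 says what the model will include, not that nothing else may enter, and section 8 defers detail to an SAP that is not at hand. That also stands. But section 8.3.3 does set out model terms, so the list can be judged on its merits.

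**The gain is assumed.** No document gives a variance, and the larger gains need nearly constant slopes. This too stands, and the size is stated accordingly.

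Three stronger readings are tempting, and the documents do not support them.
- A reader might infer that time since onset by itself is the missing covariate. It is a duration, and alone it adds almost nothing.
- A reader might infer that a chance difference in duration between arms distorts the result. If onset is spread evenly over 6-24 months, that difference has an SD of 18/sqrt(12) x sqrt(2/50) = 1.04 months. Under randomisation such imbalance is not bias, and the standard error already reflects it.
- A reader might extend the covariate to grip strength, %FVC and ALSAQ-40. Nothing was calculated for those endpoints.

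**Conclusion.** The point holds as a low-priority efficiency improvement for the primary endpoint. Section 8.3.3 names only the three minimisation factors, with a two-level screening change as their sole progression term, while onset time and baseline ALSFRS-R should be known for every subject.

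The benefit is precision only. At an SD of change of about 4 points, a fair working figure is a 4-9% fall in residual variance. It is about 1% if past and current slopes are weakly related, and more if slopes are stable. Error in the recalled onset date reduces the gain but does not bias the comparison. Every figure rests on the assumptions listed, because the protocol supplies no SD. Nothing in the protocol is contradictory, and no stated number is wrong.

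**What to change.** In section 8.3.3, or in the SAP before unblinding, add to the three factors either of the following:
- one continuous covariate, (48 - baseline ALSFRS-R)/months from onset to randomisation; or
- baseline ALSFRS-R and months since onset together, both continuous.

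Do not add months since onset alone. Choose one form in advance, because a covariate chosen after unblinding would look data-driven. Check that the eCRF keeps the onset date itself and not only a yes/no for criterion 3. The protocol lists medical history at screening but does not list onset date as a separate item.

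The cost is one sentence, one or two degrees of freedom out of about 144, and no new assessments. Leave the secondary-endpoint models as they are on this point.

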# 1412 8.3.4 Analysis of Secondary Efficacy Endpoint

- 1413 The following four secondary efficacy endpoints, the continuous data of each visit in different
- groups will be described using mean  $\pm$  standard deviation and median (minimum, maximum).
- 1415 Comparing with the baseline data, the paired T test is to be used to compare the within-group
- before-after differences. Analysis of variance (ANOVA) is to be used before and after treatment
- between groups. For the first secondary endpoint (endpoint event and disease exacerbation
- event), Kaplan-Meier plots will be used to describe the survival rate of patients without endpoint
- event, and Log-Rank test or non-parametric statistical method is to be used to compare the
- indicators of each group.
- 1421 (1) Proportion of endpoint events, including death, tracheotomy, invasive ventilator-assisted
- ventilation, or continuous non-invasive ventilator-assisted ventilation ( $\geq$  22 h per day for  $\geq$
- 1423 10 days);
- 1424 (2) Difference between the groups in grip strength change from baseline at Day 180;
- 1425 (3) Difference between the groups in respiratory function (%FVC) change from baseline at
- 1426 Day 180;
- 1427 (4) Difference between the groups in ALSAQ-40 scores change from baseline at Day 180.
- 1428 **8.3.5 Safety Assessment**
- Descriptive statistical analysis is mainly to be used to list the AE and SAE, drug-related AE and
- SAE that occurs in this trial, and between-group comparisons are conducted using the  $X^2$  test or
- 1431 Fisher's test.
- 1432 Descriptive statistics are to be used to summarize laboratory tests, vital signs, and
- electrocardiograms, etc. Shift tables are to be used to describe changes in normal/abnormal
- results before and after administration, such as laboratory tests, electrocardiograms, and physical
- 1435 examinations.
- 1436 **8.3.6 Interim Analysis**
- 1437 Not Applicable

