# **Secondary Endpoints:**

✓ Difference between the groups in the proportion of events such as death, tracheotomy, invasive ventilation, or continuous non-invasive ventilation ( $\geq 22$  h per day for  $\geq 10$  days);

	✓ Difference between the groups in gripe strength change from baseline at Day 180;
	✓ Difference between the groups in respiratory function (%FVC) change from baseline at day 180;
	✓ Difference between the groups in ALSAQ-40 scores change from baseline at Day 180.
	Safety evaluation including: adverse events (AEs), serious adverse events (SAEs), clinical laboratory tests (hematology, urinalysis, blood biochemistry, thyroid function), vital signs (blood pressure, respiratory rate, pulse and body temperature), 12-lead electrocardiogram (ECG) examination, physical examination.
	Primary safety indicators:
Safety Assessment Indicators	Percentage of subjects with serious adverse reactions within 180 days; (Adverse reactions: AEs related to the IMP)
	Secondary safety indicators:
	Percentage of subjects with adverse reactions within 180 days;
	AEs, SAEs, and their incidence, the clinical manifestations, severity, time of occurrence, end time, duration, treatment measures and outcomes of these are to be recorded, and the correlation between AE and IMP are to be determined.
PK/PD and Biomarkers	The cerebrospinal fluid (Tmax after administration, optional) is to be taken (in part of subjects) at baseline period before administration and 180 days after administration, and the concentration of TBN and its metabolites in cerebrospinal fluid and plasm are to be measured for PK/PD analysis. Biomarkers, such as 3-NT, 8-OHdG, NFL levels in cerebrospinal fluid are to be determined.
Treatment	Subjects need to terminate the treatment permanently if the following events occur:
Termination Termination	✓ The subject is pregnant;
	✓ The subject withdraws informed consent;
	✓ The subject has a medical emergency that requires to terminate the

	treatment permanantly, such as death, tracheotomy, invasive ventilator assisted ventilation, or continuous non-invasive ventilator assisted ventilation (≥ 22 h per day for ≥10 days);  ✓ The subject has a medical emergency requiring a unblinding of the treatment of the subject;  ✓ Determinations based on medical reasons made by investigator.

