#### 3.3 Study Endpoints and Schedule

# 638 **3.3.1 Efficacy Endpoints**

- 639 ✓ Difference between the groups in the ALSFRS-R scores change from baseline at Day 180.
- 640 ✓ Difference between the groups in the proportion of events such as death, tracheotomy,
- invasive ventilator assisted ventilation, or continuous non-invasive ventilator assisted
- ventilation ( $\geq 22$  h per day for  $\geq 10$  days).
- 643 ✓ Difference between the groups in grip strength change from baseline at Day 180.
- of 544 ✓ Difference between the groups in respiratory function (%FVC) change from baseline at day
- 645 180.

637

of 546 ✓ Difference between the groups in ALSAQ-40 scores change from baseline at Day 180.

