#### 1372 **8.2** Analysis Population

- 1373 This study used three data sets: Full Analysis Set, Per-Protocol analysis set, and Safety analysis
- 1374 set.
- 1375 Full Analysis Set (FAS): A collection of all randomized subjects with at least one study
- administration and at least one valid post-dose efficacy evaluation data. FAS is the primary
- analysis set. The FAS will be used to analyze the subject's distribution, demographic data, and
- 1378 baseline characteristics and efficacy. Subjects will be analyzed according to their randomized
- 1379 groups.
- Per-Protocol Set (PPS): It included FAS subjects who meet the main inclusion criteria and do not
- meet the main exclusion criteria, complete the treatment without any major protocol deviations.
- The PPS is mainly used for the sensitivity analysis of efficacy.
- Safety analysis set (SS): A collection of subjects with at least one administration and actual
- safety data of the post study administration. Missing safety values are generally not carried
- forward. SS will be used for safety analysis. Subjects will be analyzed according to randomized
- 1386 groups.

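### The full analysis set can drop an early death from the secondary endpoint that counts deaths, and Section 8.3.4 labels and analyses that endpoint differently from its definition

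*Protocol*

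**What the plan says.** **Definition.** The endpoint is defined three times, each time as a proportion with the same four components (death, tracheotomy, invasive ventilation, prolonged non-invasive ventilation).

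- Synopsis, Secondary Endpoints: "Difference between the groups in the proportion of events such as death, tracheotomy, invasive ventilation, or continuous non-invasive ventilation".
- Section 3.3.1: "Difference between the groups in the proportion of events such as death, tracheotomy", followed by the two ventilation components.
- Section 8.3.4, item (1): "Proportion of endpoint events, including death, tracheotomy, invasive ventilator-assisted", followed by the rest of the list.

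**Analysis.** The text above that list in Section 8.3.4 introduces the endpoint as "For the first secondary endpoint (endpoint event and disease exacerbation" event. It then describes it by Kaplan-Meier: "event), Kaplan-Meier plots will be used to describe the survival rate of patients without endpoint" event. The groups are compared as follows: "event, and Log-Rank test or non-parametric statistical method is to be used to compare the" groups. No comparison of proportions is given.

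**Analysis set.** Under Section 8.2 the FAS takes randomised subjects with at least one "administration and at least one valid post-dose efficacy evaluation data. FAS is the primary" analysis set. It is the set used for "baseline characteristics and efficacy. Subjects will be analyzed according to their randomized" groups.

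**Timing.** In the Trial Schedule and Section 3.5.3, the first planned ALSFRS-R, grip strength and %FVC after dosing are at Day 30 ± 3. Day 7 is a phone visit without efficacy measures.

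**Safety recording.** Section 6.3.3 has a death confirmed as due to disease progression entered in the eCRF but not as an SAE.

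**The concern.** A condition that can be met only after randomisation decides who enters the analysis, and here it is tied to the outcome. Death before the first assessment is what prevents the assessment. If such deaths differ between arms, removing them flatters the arm that has more of them. If they do not differ, the event counts are still understated. The safety tables may not recover the case, because a progression death is kept out of the SAE count.

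The label matters separately. The entry criteria require measurable decline, so many subjects can be expected to worsen over six months. If an undefined exacerbation event were counted, the composite could be a different endpoint. The open wording of the definitions in the Synopsis and Section 3.3.1 (*such as*) leaves the same door ajar. Finally, the quantity named as the endpoint, a between-group difference in proportions, has no stated estimate or test.

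**Working it through.** The protocol states no event rate, power or event count for this endpoint, so there is no figure of its own to reproduce. The check is a reading of the rules, followed by an illustration of size.

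**Step 1: follow a dosed subject who dies on, say, Day 20.**
- Randomised and dosed: yes.
- ALSFRS-R, grip or %FVC after dosing: none, since the first is scheduled at Day 30 ± 3.
- Withdrawal visit (Section 3.5.5; Trial Schedule note, 7 to 14 days after the last dose): impossible after death.
- Does the death itself qualify as an efficacy evaluation? Section 8.2 does not say.
- Result: on a literal reading the subject is outside the FAS and is not even a censored observation in the Kaplan-Meier analysis.

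**Step 2: follow a subject who is ventilated on Day 20 and survives.** The withdrawal visit includes ALSFRS-R, grip and %FVC. If it takes place, the subject is in the FAS. If it does not, the position is that of Step 1.

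**Step 3: how many events could be affected.** Inputs: 50 per arm (Section 8.1); 180-day event proportion p (assumed, 5 to 20%); constant hazard (assumed).

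Events before Day 30 per arm = 50 × [1 − (1 − p)^(30/180)]

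| Assumed p | Events by Day 180 per arm | Events before Day 30 per arm | Share of all events |
|---|---|---|---|
| 5% | 2.5 | 0.43 | 17% |
| 10% | 5.0 | 0.87 | 17% |
| 15% | 7.5 | 1.34 | 18% |
| 20% | 10.0 | 1.83 | 18% |

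Under these assumptions the third column is an upper bound on losses, because it counts all events and only deaths, or events without a withdrawal visit, are lost.

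**Step 4: what one lost death does.** At p = 10% an arm has 5 events in 50 subjects, or 10.0%. Excluding one death removes it from numerator and denominator: 4/49 = 8.2%. The arm's proportion falls by 1.8 percentage points and 1/5 = 20% of its events disappear.

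**Step 5: the open choice of test.** In a null simulation (three arms of 50, 3000 runs per setting, p of 10% or 20%, dropout of none or 20%), taking the better of log-rank and Gehan-Wilcoxon rejects in 5.0 to 5.4% of runs. Adding a chi-square test on proportions gives 5.4 to 5.7%. The tests use the same events and are highly correlated, so the inflation is slight.

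**The case against.** **Few subjects are at risk.** Entry requires %FVC of at least 80%, full respiratory scores, every ALSFRS-R item at 2 or more, and onset within two years. Deaths in the first month should be rare. This stands and limits the size of the problem, though it does not repair the rule.

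**The event might already count.** Section 3.3.1 lists the composite among the efficacy endpoints, so a recorded event could be read as an efficacy evaluation, and Section 3.5.3.1 allows extra visits. Both are possible readings. The protocol states neither as the FAS rule, and an extra visit helps only if it precedes the death.

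**Details belong in the SAP.** Section 8 promises one, and the choice of test is commonly left to it. That is fair for the test, which is the weakest part. The analysis set, the label and the definitions are written in the protocol itself.

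**Kaplan-Meier yields a proportion.** True: a Day 180 estimate from the curve would match the definition. Section 8.3.4 does not ask for that estimate or for a between-group difference.

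**Stronger readings a reader might infer.**
- That the survival curve is free of exacerbation events as well. The text describes the curve only for patients without an endpoint event; the extra term stands in the parenthetical label.
- That all subjects ventilated early are lost. The withdrawal visit can keep survivors.
- That the open choice of test seriously inflates type I error. Step 5 shows that it does not.

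**Conclusion.** The point holds in a limited form. As written, the FAS rule allows a dosed subject who dies before about Day 30, or who has an event and no withdrawal visit, to be left out of the analysis of that same event. A death attributed to progression could be absent from the SAE comparison too, although it would still be in the eCRF. Alongside this, Section 8.3.4 names an undefined component and gives no comparison of the proportion that the endpoint is.

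The expected loss is small: at most about 0.4 to 1.8 events per arm under assumed 180-day rates of 5 to 20% and a constant hazard. The consequence for a sparse endpoint is not trivial, since one lost death is a fifth of an arm's events at an assumed 10% rate. The event rates are assumptions; the protocol offers none. This is a secondary endpoint in an exploratory phase 2 trial, so the matter calls for a clear correction of wording. It does not undermine the primary analysis.

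**What to change.** 1. In Section 8.2 or 8.3.4, state that this endpoint is analysed in all randomised and dosed subjects, by randomised group, with no requirement for an efficacy measurement after dosing.
2. Close the event list to the four named components: remove *such as* from the Synopsis and Section 3.3.1, and delete the exacerbation term from the label in Section 8.3.4.
3. Report Kaplan-Meier event proportions at Day 180 with between-group differences, so that the analysis estimates the defined proportion. Name log-rank as the single test and delete the unnamed alternative.

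The cost is protocol and SAP wording only. No visit or assessment is added, and Section 6.3.3 already has progression deaths recorded in the eCRF.
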